11.10 Pass/fail criteria

To demonstrate superiority of the investigational device, the null hypothesis of the primary endpoints must be rejected, at a 5% significance (alpha 0.05).

The pass criteria for the study are based on the results from analysing the two primary endpoints in a hierarchical fashion: rejecting the null-hypothesis on the first endpoint (Residual urine at first flow-stop) before continuing to the second (Number of flow-stop episodes).

12 Data management

12.1 Data collection and data management

12.1.1 Data Collection in the clinical investigation

Data management and statistical analyses are carried out by Medical Affairs, Coloplast A/S.

Data will be collected through an electronic data capturing (EDC) system on electronic Case Report Forms (eCRF), a secure, internet-based case report form. This system will be used to record all subject information collected in the investigation for secure data tracking and centralised data monitoring (“remote monitoring”) done by monitors, as defined in the monitoring plan.

The EDC system used is Rave EDC, version 20121.1.4, delivered by Medidata Solutions Inc. The system is designed to be compliant with the FDA requirements of 21 CFR part 11. It is a validated data management system allowing only qualified and trained personnel to enter the system. The system has full audit trail and electronic signature.

The sponsor will be responsible for training the investigator or delegate, in completion of the eCRF.

Principal Investigator, or delegate, at the clinical site will perform primary data collection directly into the eCRF or drawn from source-document (i.e. paper CRF, medical records etc. according to the Source Data

Specification Form) reviews. The eCRF will be completed on a continuous basis starting from the point of enrolling the subject to final follow up.

The eCRF will be completed by the investigator, or delegate, who have signed the Site Personnel Signature and Delegation List and Clinical Investigation Training Log. It will be the responsibility of the investigator to ensure that all measurements and observations are correctly noted in the eCRF.

All assessments and observations throughout the investigation for each subject must be carefully recorded in an eCRF during the visit or immediately after. The eCRF makes it possible to enter data right away when they are obtained. This is the preferred way of collecting data. In case this is not possible the data should be entered no later than 7 days after the visit / procedure.

Subject reported outcomes (Perception questionnaire, the quality-of-life questionnaire (Qualiveen), VAS scale and dipstick results during the two weeks of home use) will be completed by the subject in a paper CRF and entered into the eCRF by site personnel. After completion of the VAS scale by subject, the site personnel will measure the VAS-scale and enter the measurement in the eCRF.

Data from urine analysis will be batch uploaded into the EDC system.

Data derived from the catheterisation profile will be batch uploaded into the EDC system.

Raw data from the scale/balance and from the pressure sensor are stored in the electric boxes and copied on USB sticks. The USB sticks are sent to Coloplast A/S via courier. Raw data from either the USB sticks or the electric box are then analysed by two specialists independently.

A calibration/comparison is then performed between the two specialists and an excel sheet is made combining the relevant data. The excel sheet is thereby uploaded to an allocated SharePoint.

Adverse events should be registered following the timelines described in the Adverse Event section.

In the unforeseen situation, where site cannot establish connection to the EDC system a paper CRF (pCRF) has been printed and supplied by sponsor.

The investigator will keep a separate list of the subjects' ID numbers, names and addresses in a locked room/cabinet. Only data referred to in this clinical investigation plan will be recorded in the CRFs.

12.1.2 Database Management, Queries and Quality Control

The data management system has restricted role-based access control. The principal investigator or delegate must be trained in the system prior to getting access. The training is web-based and must be completed before access to the investigation is granted. Training will be documented in the data management system. Only the principal investigator, or delegate, will be authorised to enter data in the eCRF.

The monitor, using his/her personal login information shall verify all critical data points against the source documents and issue electronic queries for the authorised clinical site personnel to respond, as defined in the monitoring plan.

The principal investigator, using his/her personal login information shall sign each eCRF.

Automated, real-time access to the data enable control on study compliance and safety assessments.

A critical quality control will be performed by the sponsor's data management team and queries issued where needed. Such queries will be reviewed by the monitor and must be resolved by the site personnel.

At the end of the study a formal data review meeting will be performed before the database will be locked.

A full audit trail ensures, that each user's (site personnel, monitor, sponsor, data manager) access to and actions in the system is tracked.

The Data Management Procedures are further described in the Data Management instructions.

12.2 Data retention

The Investigator file must be archived for a minimum period of 10 years after the final clinical investigation report has been signed.

13 Amendments to the Clinical Investigation Plan

No changes in the clinical investigation procedures shall be affected without mutual agreement between the principal investigator and the sponsor. The agreement of the changes must be documented by signing the corresponding clinical investigation plan amendments and registered in the Change Log.

All significant changes require notification to the Ethical Committee and applicable regulatory authority. Substantial changes may require approval from the Ethical Committee and applicable regulatory authority prior to implementation.

14 Deviations from the Clinical Investigation Plan

Deviations to the Clinical Investigation Plan occurs when the activities during the clinical investigation do not comply with the Ethical Committee and applicable regulatory authority approvals.

A minor deviation is defined as those that don't increase risk or decrease benefit or don't have a significant effect on the subject's rights, safety or welfare; and/or on the integrity of the data. If a deviation increases risk or decreases benefit and/or; has a significant effect on the subject's rights, safety or welfare and/or has a significant effect on the integrity of the data it is defined as a major deviation and the Investigator must inform the monitor immediately, and the Monitor will report and inform the Clinical Manager or designee immediately.

The investigator is not allowed to deviate from the Clinical Investigation Plan unless, under emergency circumstances or to protect the rights, safety, and welfare of the subject(s).

For the purposes of this investigation, any variance from the protocol is considered a deviation and is to be reported.

The site will complete a deviation eCRF form for all data-related deviations and all deviations that are not related to the data (for example, an untrained nurse performing study procedures) are reported by the monitor in the Periodic Monitoring Site Report and actions are addressed to the Investigator for completion.

If any deviations to the investigation plan are detected during the monitoring visit, the Monitor shall ensure the site reports all deviations in the eCRF or on the Deviation log in the Investigator File. Additionally, the monitor must report any deviation noted during the visit in the Periodic Monitoring Report.

Monitor will align with data management in each investigation, how data management will be informed about all deviations.

The following information about the deviation will be collected:

- Site ID
- Subject ID
- Date the deviation took place
- What the deviation is related to

- If the deviation affects data integrity
- If the deviation affects subject safety
- Supplementary description of the deviation
- Actions taken with regards to the deviation

15 Device Accountability

All access to the investigational devices used in the clinical investigation is controlled by storage procedures and device accountability logs as described below. The investigational devices must only be used in this clinical investigation and only according to the CIP.

Sponsor keeps a device accountability log that states the physical location of all investigational devices from shipment of investigations devices to the investigational sites until return of or disposal.

The principal investigator or an authorized designee keeps records documenting the receipt, use and return and disposal of the investigational devices, which includes:

- Subject identification
- Identification of each investigational device (batch no./serial no./unique code)
- The expiry date, if applicable
- The date(s) of use, if possible
- The date on which the investigational device was returned from the subject
- Number of devices handed out to subject

16 Statement of compliance

The clinical investigation is conducted in accordance with:

- The investigation is conducted in accordance with 'The Declaration of Helsinki', 1964, last amended at the 64th WMA General Assembly, Fortaleza, Brazil, October 2013
- MDR (EU) 2017/745
- ISO 14155:2020 "Clinical Investigation of medical devices for human subjects – Good clinical practices".
- Any applicable regional or national regulations will be specified in the country specific CIP.

16.1 Ethics committee and regulatory authorities

The CIP and/or other relevant documents are submitted to the appropriate EC(s) and regulatory authorities. This clinical investigation will not begin until the required approval from the EC and regulatory authorities have been obtained. Any amendment to the protocol will be submitted to the same EC(s) and regulatory authority.

Sponsor will notify the relevant regulatory authority and EC(s) concerned of the end of the clinical investigation.

16.2 Other relevant authorities

National requirements for submission to committees and authorities will be followed.

16.3 Data protection

As part of the investigation Coloplast A/S, [name], Denmark ("Coloplast") will collect and process the personal information the subject provides for the investigation ("subject personal data"). This

includes identification and contact information (which may be anonymised depending on the nature of the investigation) as well as information about device usage experience and your health. Coloplast will comply with the EU General Data Protection Regulation (GDPR) and the Danish act on data protection ("databeskyttelsesloven"), including in connection with transfer of data to third countries, cf. chapter V of GDPR, Coloplast will only process the subjects' personal data:

1. To conduct the investigation and carry out related research based on subject consent (primary use), cf. articles 6(1)(a) and 9(2)(a) of GDPR,
2. To comply with applicable legal obligations to e.g. ensure reliability and safety, cf. article 6(1)(c) in conjunction with article 9(1)(i) of GDPR, and
3. If separate consent is given for secondary use of subject personal data, cf. articles 6(1)(a) and 9(2)(a) of GDPR – carry out research outside the clinical protocol to improve Coloplast's devices and services, and for use in education.

Part of Coloplast's processing is carried out on third-party platforms (clinical trial databases) and certain third parties are assisting Coloplast in the processing (e.g. the investigator). Such cases will imply a transfer of your personal data to the third parties, but solely for the specified purposes and with the third parties acting on instruction from Coloplast. Data may be collected and processed across the Coloplast network, which may entail processing of personal data outside the European Economic Area. In such cases, an adequate level of protection will be ensured by the third parties being subject to the standard contractual clauses on data protection adopted by the EU or to an EU-approved certification mechanism on data protection. For further information about this please the subject can always consult Coloplast's data protection officer (details below).

Subject personal data will be kept as long as required under applicable laws and regulations. The EU Medical Device Regulation obligates Coloplast to keep the data for a period of at least ten years after the investigation is completed, or, in the event that the device is subsequently placed on the market, at least ten years after the last device has been placed on the market. Subject personal data will be deleted at the end of the mandatory retention period.

If the subject has questions or queries regarding Coloplast's handling of personal information, the subject can always contact Coloplast's Data Protection Officer at [contact]. Complaints related to Coloplast's handling of subject personal information may similarly be sent to the Data Protection Officer, and the subject is also entitled to file a complaint with the relevant supervisory authority, which in the case of Denmark is the Danish Data Protection Agency (www.datatilsynet.dk).

The subject can write to [contact] at any time to request:

- Access to personal data
- Correction of errors in personal data or to erase personal data
- Limit what can be done with personal data
- To receive personal data in machine-readable format (data portability).
- Withdrawal of consents the subject has given Coloplast to process personal data

16.4 Indemnity

All subjects are fully covered by Coloplast A/S insurance throughout the investigation. Insurance has been signed with:

XL Insurance Company SE
[name]
[name]
[contact]

16.5 Financial conditions

Coloplast A/S will compensate all investigators involved in the clinical investigation for their time and resources spent on the investigation. All financial agreements with the investigation sites involved in the clinical investigation will be specified in a sponsor investigator agreement.

17 Informed consent process

Written informed consent is obtained from all subjects participating in the investigation after thorough written and verbal information. The information is given by the investigator or his/her representative in the subjects' native non-technical language. Each subject will be fully informed about the aim of the investigation, procedures, potential risks, or inconveniences and/or expected benefits and all anticipated adverse device effects and ensure ample time is provided before deciding on participation. The subjects will be informed that their participation is voluntary and that they may leave the investigation at any time, without this having any influence on their further treatment.

The informed consent signature form includes personally dated signatures of the subject and the PI or his/her representative responsible for conducting the informed consent process. A copy will be provided to the subject.

If new information is to be given during the investigation, sponsor will inform the investigators, and the new information is given to the subjects by the investigator. If new information becomes available that can significantly affect a subject's future health and medical care that information will be provided to the subject in written form. CM is responsible for writing the information and providing the approved Subject Information and Consent Form to investigators that will further provide it to the subjects. If applicable, all affected subjects shall be asked to confirm their continuing informed consent in writing.

This procedure also applies to informed consent obtained from a subject's legal representative. The procedure cannot waive the subjects' legal rights.

18 Subject compensation

18.1 Compensation in case of injury

Device liability and No-Fault Clinical Investigation Insurance covering the duration of the clinical investigation are in place, to enable compensation in the event of an injury to a participating subject.

18.2 Compensation for participating in the clinical investigation

Subjects will be compensated with a voucher per visit, paid by Coloplast A/S with the value as described below:

	Subjects
[REDACTED]	[REDACTED]

This is to compensate for any inconvenience caused during the catheterisations, time used. Travel expenses will be accounted for separately. For Danish subjects, the remuneration/vouchers are taxable (B-income) and it is the responsibility of the subject to declare this to SKAT.

19 Adverse events, adverse device effects and device deficiencies

19.1 Adverse events

An adverse event is any untoward medical occurrence, unintended disease or injury, or untoward clinical signs (including abnormal laboratory findings) in subjects, whether related to the investigational medical device(s) or the comparator(s), or the procedures involved. The adverse event shall be marked with the intensity mild, moderate, or severe. This could include events such as headache or dizziness.

19.2 Adverse device effect

An adverse event, which is related to the use of the investigational medical device, is an adverse device effect, and should be marked as unlikely related, possible related, probable related or with causal relationship on the adverse event form.

The definition of an adverse device effect includes any event resulting from insufficiencies or inadequacies in the instruction for use, deployment, or any malfunction of the medical device, as well as any event resulting from use error or from intentional misuse of the device.

Table 2 lists anticipated adverse device effects that may occur.

Table 19-1 Anticipated adverse device effects and their likely incidence rates

ANTICIPATED ADE	INCIDENCE RATE
Urinary tract infection	Very unlikely
Macroscopic haematuria	Unlikely
Macroscopic leukocytes	Unlikely
Stinging and pain in urethra during catheterisation	Likely
Irritation of mucosa	Likely

19.3 Device deficiency

A device deficiency is the inadequacy of the investigational medical device or comparator with respect to its identity, quality, durability, reliability, usability, safety, or performance. This includes malfunctions, use errors and inadequacy in the information supplied by the manufacturer including labelling.

19.4 Serious adverse events (SAE)

A serious adverse event is an adverse event that:

- Led to death,
- Led to a serious deterioration in the health of the subject, users or other persons as defined by one or more of the following:
 - 1) a life-threatening illness or injury, or
 - 2) a permanent impairment of a body structure or a body function including chronic diseases, or
 - 3) in-patient or prolonged hospitalization, or
 - 4) medical or surgical intervention to prevent life-threatening illness or injury or permanent impairment to a body structure or a body function.
- Led to foetal distress, foetal death, a congenital abnormality, or birth defect including physical or mental impairment.

This includes device deficiencies that might have led to a serious adverse event if:

- 1) Suitable action had not been taken, or
- 2) Intervention had not been made, or

3) Circumstances had been less fortunate.

These are handled under the serious adverse event reporting.

Planned hospitalization for a pre-existing condition, or a procedure required by the CIP, without serious deterioration in health, is not considered a serious adverse event.

19.4.1 Serious adverse device effect (SADE)

A serious adverse device effect is an adverse device effect that has resulted in any of the consequences characteristic of a serious adverse event.

19.4.2 Anticipated serious adverse device effect (ASADE)

There are no anticipated SADEs.

19.4.3 Unanticipated serious adverse device effect (USADE)

An unanticipated serious adverse device effect is a serious adverse device effect which by its nature, incidence, severity, or outcome has not been identified in the current version of the risk analysis report.

19.5 Medical care of subjects

Principal investigator shall ensure that adequate medical care is provided, during and after participation in the clinical investigation, to a subject experiencing an adverse event. All ongoing ADEs, SAEs, SADEs and DDs that could have led to a SAE at subject termination will be followed according to the Risk Benefit analysis (see section 9). An ongoing adverse event at subject termination visit is documented as the current status for the adverse event and will not be followed up.

The subjects shall be informed of any new significant findings occurring during the clinical investigation, including the need for additional medical care that can be required, and of the nature and possible cause of any adverse events experienced.

19.6 Reporting and timelines

All adverse events and device deficiencies will be reported in the eDC, Rave database. If, for some reason, the system is off-line, investigators (or designee) are required to report the event to: **[contact]**.

19.7 Investigator's reporting responsibilities

PI at each site must assess all (S)AE's that occur at his/her site.

- All serious adverse events and serious adverse device effects must be reported to sponsor within 24 hours of the site becoming aware of the event.
- A device deficiency that could have led to a serious adverse event but did not because suitable action was taken, intervention had been made or because of fortunate circumstances should be reported to sponsor within 24 hours of the site becoming aware of the event.
- New findings and/or updates in relation to already reported serious events should also be reported to sponsor within 24 hours of the site becoming aware of the event.
- Device deficiencies and all adverse device effects related to CE marked Coloplast investigational device and/or comparator must be reported to sponsor within 24 hours of becoming aware of the event.

When reporting the SAE, the relationship to the test material shall be described whether the event is considered

- **Not related**, the event has no temporal relationship with the use of the test material or the procedures.
- **Unlikely related**, the relationship with the use of the test material seems not relevant and/or the event can be reasonably explained by another cause, but additional information may be obtained.
- **Possible related**, the relationship with the use of the test material is weak but cannot be ruled out completely. Alternative causes are also possible (e.g. an underlying or concurrent illness/ clinical condition or/and an effect of another device, drug or treatment). Cases where relatedness cannot be assessed, or no information has been obtained should also be classified as possible.
- **Probable related**, the relationship with the use of the test material seems relevant and/or the event cannot reasonably be explained by another cause, but additional information may be obtained.
- **Definitely related/Causal relationship**, the event has a temporal relationship with the test material use/application or procedures.

and the intensity of the event should be considered, as such:

- **Mild**, the intensity of the event is mild with no further action or intervention
- **Moderate**, the intensity of the event will lead to an action or intervention to solve the event
- **Severe**, the intensity of the event will lead to follow up on the action or intervention, as the effect of the action or intervention may not decrease the symptoms.

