5.7 Total number of devices intended for the clinical investigation

Seventy-two subjects will be included in the study. The test period (home-use) is 4 weeks (28 days) and with a use of 6 catheters/day, the total use is 12.096 units.

Table 5-1 presents an overview of devices needed in this investigation.

Table 5-1: Overview of devices needed in the investigation

Device	Description
Investigational device 1	Intermittent catheter for male use – size CH12
Investigational device 2	Intermittent catheter for male use – size CH14
Investigational device for hospital assessments	Investigational device to be used for hospital assessments will be provided by Coloplast A/S
Comparator device for hospital assessments	Comparator device to be used for hospital assessments will be provided by Coloplast A/S

Use of catheters during study visits will be 72 subjects conducting three visits, using two catheters per visit resulting in a total of 432 units.

A 20%-buffer is added accounting for different sizes, number of sites, etc. Therefore, 15.034 units are required, split per size and country as follows if subjects are equally split between participating countries:

Size/Country	Germany	Denmark	France	United Kingdom
CH12	1880	1880	1880	1880
CH14	1880	1880	1880	1880

Please note that the numbers are estimates.

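### The two end categories of the 19.7 causality scale rest on undefined timing alone, so they overlap the middle categories and, with 19.2, can inflate and blur adverse device effect coding

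*Combined protocol and SAP*

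**What the plan says.** Section 19.7 gives a five-step relatedness scale for use when a serious adverse event is reported.

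- *Not related* needs only one thing: "the event has no temporal relationship with the use of the test material or the procedures".
- The next step up, *Unlikely*, turns on a different question: "the relationship with the use of the test material seems not relevant and/or the event can be reasonably explained by another cause".
- *Possible* is for cases where "the relationship with the use of the test material is weak but cannot be ruled out completely". Other causes are allowed, and this is also the default when relatedness cannot be assessed.
- *Probable* applies if the link seems relevant, and/or no other cause reasonably explains the event.
- *Definitely related/Causal relationship* goes back to timing: "the event has a temporal relationship with the test material use/application or procedures".

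Section 19.2 defines an adverse device effect (ADE) as an adverse event related to use of the investigational device, and says that it "should be marked as unlikely related, possible related, probable related or with causal relationship on the adverse event form". Only *Not related* is absent from that list.

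On frequency of use, section 5.7 plans supply "with a use of 6 catheters/day, the total use is 12.096 units". Section 8.5 leaves actual home use to each man's own regime.

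**The concern.** A causality scale should ask for more evidence of causation at each step. This one changes its criterion at both ends. The middle three steps weigh relevance, strength and other explanations. The outer two ask only whether the event and the exposure are linked in time. In men who catheterise several times a day, almost any event is close in time to a use, so timing separates little.

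The label has consequences:

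- An ADE with a serious outcome becomes a serious ADE (19.4.1).
- Under 8.10, ADEs still open at termination are followed until resolution. Under 19.5, an ongoing adverse event outside the listed classes is recorded at its current status and not followed.
- The device is not CE-marked (5.1). Relatedness is the main way a reader of the safety listing separates device harm from background illness.
- With 8–11 sites in up to four countries (section 7), two sites could code the same event at opposite ends of the scale and both be following the text.

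**Working it through.** **The wording, tested on one event.** Take a hospital admission for an illness with an obvious cause unconnected with the catheter, starting two hours after a catheterisation. Suppose the investigator accepts two hours as a temporal relationship.

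- *Not related*: fails, because there is a temporal relationship.
- *Unlikely*: met, because another cause reasonably explains the event.
- *Probable*: fails, because the link does not seem relevant and another cause does explain the event.
- *Definitely*: met, because a temporal relationship is all it asks for.

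The event qualifies for the second and fifth steps and fails the fourth, so the scale is not ordered. No rule says which label wins. Either label is on the 19.2 list of ADE markings, although 19.7 describes the lower one as a link that does not seem relevant.

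**How often timing is present.** First, the plan's own figures reproduce:

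- Home use: 72 × 28 × 6 = 12,096 units, as stated.
- Visit use: 72 × 3 × 2 = 432 units, as stated.
- With the 20% buffer: (12,096 + 432) × 1.2 = 15,033.6, stated as 15,034.

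The mean gap between uses is 24/k hours for k uses a day. At k = 6 it is 24/6 = 4 h. For an assumed 4 to 8 uses a day it is 6 h to 3 h.

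The text gives no window for a temporal relationship, so the window w has to be assumed. With even spacing, the share of home time within w hours after a use is min(1, w × k/24). At k = 6:

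- w = 0.5 h: 0.5 × 6/24 = 12.5%
- w = 1 h: 25%
- w = 2 h: 50%
- w = 4 h: 100%

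If one gap is an 8-hour night, the other five are 16/5 = 3.2 h each. The 4-hour share is then (4 + 5 × 3.2)/24 = 20/24 = 83%, and the 8-hour share is 100%.

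Across 4 to 8 uses a day with even spacing, the half-hour share is 8% to 17% and the 4-hour share is 67% to 100%.

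**What lies outside.** Of about 63 study days, 28 (44%) are comparator use and up to 7 (11%) fall outside the two home periods. In the comparator-first sequence no investigational device has been used through the first period.

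**The case against.** Much of the case on the other side stands.

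- *The label of the top category contains the word causal.* A sensible investigator may read timing as an addition to that label. But the definition is what sites are trained on, and it adds nothing about cause.
- *The 19.7 scale is introduced for serious events.* Applying it to the headache or dizziness named as examples in 19.1 is therefore an inference. It is a reasonable one, since 19.2 puts the same labels on the adverse event form without defining them, but it is not stated.
- *Serious events are protected.* They go to the sponsor within 24 hours (19.7) and to authorities within 7 days (19.8) whatever the label. Under 19.5, serious events are among the classes still followed after termination. Section 20 has no trigger based on ADE counts.
- *Over-attribution is the cautious direction*, and counting *unlikely* as an ADE could be deliberate. If so, it still conflicts with how 19.7 describes that category.
- *Probable uses and/or*, so absence of another cause is not strictly required. It still demands one causal judgement, and *Definitely* demands none.

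A reader might go further and infer that *Not related* can never be used, that *Definitely* is automatic, or that every adverse event becomes an ADE. The documents do not support this. The middle categories stay open to an event with a temporal link. *Not related* remains available before first use or under a narrow window. Section 19.2 admits only events related to the investigational device, which excludes the first period in comparator-first men. Six a day is a supply estimate, and any claim of 100% coverage depends on the assumed window.

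**Conclusion.** The defect holds as one of overlap and order. Both end categories turn on an undefined temporal relationship, *Definitely* has a weaker written test than *Probable*, and one event can satisfy *Unlikely* and *Definitely* together. During investigational-device use this can inflate ADE and serious ADE classification and make it inconsistent between sites. Its size cannot be fixed from the documents: the share of home time that counts as temporally related depends entirely on the window a site adopts.

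The practical effect is on safety classification and on which non-serious events are followed after termination. Adverse events are only listed and/or summarised (11.7), so no efficacy endpoint, alpha, power figure or pass criterion changes. The point should be corrected, but it does not threaten the primary conclusion.

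**What to change.** 1. In 19.7, let *Definitely related* require a temporal relationship, a plausible device or procedure effect, and no other reasonable cause. Let *Not related* mean no temporal relationship, or an event clearly explained by another cause.
2. Make the five categories mutually exclusive. State what counts as a temporal relationship, how a clear other cause (*Not related*) differs from a reasonable one (*Unlikely*), and which label applies if two still fit.
3. Reconcile 19.2 with 19.7 on whether *unlikely related* counts as an ADE, and give the reason for the choice.
4. State that the scale applies to every adverse event on the form, not only to serious ones.

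The cost is a wording change in two sections and in the eCRF help text. The small downside is that events already classified would have to be re-coded.
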